### Endpoints

**Primary:** Study to end when sample sizes are obtained.

**Secondary:** None.

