## Research Question and Aims

Hypothesis: A pre-ICU simulation session will decrease the incidence and severity of post-operative delirium in the ICU after an elective cardiothoracic surgical procedure.

Aims, purpose, or objectives: The purpose of this project is to evaluate the effect of a pre-ICU admission simulation session on post-operative delirium in the elective cardiothoracic surgical population,

Background (*Include relevant experience, gaps in current knowledge, preliminary data, etc.*):

Cardiothoracic patients are at a high risk for post-operative delirium in the intensive care unit (ICU). Approximately 50% of patients admitted to the intensive care unit develop or are impacted by some form of acute delirium. This can lead to a three-fold increase in 6-month mortality, increased time on the mechanical ventilator, elongated hospital length of stay, and nearly 50% of those patients affected having a cognitive impairment at hospital discharge some with long term cognitive impairment (approximately 1 in 3 patients). Specifically, delirium incidence in the post-cardiac surgery population is between 26-52%. Delirium in this population specifically has been associated with increased mortality, stroke risk, hospital readmission and cognitive dysfunction as well as poorer functional status.

The literature supports the use of pre-operative educational experiences as a mechanism to reduce delirium incidence.

The initial phase of this project is to identify the baseline rate of delirium in the cardiothoracic surgical intensive care unit. Anecdotal data from practitioners in this unit indicate that post-operative delirium across “surgical procedure types” is a strong concern. A primary gap in this population’s care is that our institution does not have a program in place to prepare patients for the experience they will have admitted to the ICU post-operatively.

The initial phase of this project will include baseline data collection over a period of 3 months to determine current delirium rates (CAM-ICU) and other ICU outcome metrics including ventilator time, use of sedatives and antipsychotics, restraint use rates, and ICU and hospital length of stay.

Following initial baseline data collection, the intervention will be to provide a pre-cardiothoracic surgery patient a multi-sensory pre-recorded virtual reality ICU simulation experience to introduce them to the senses they can

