## Study Design and Methods

**Methods:** *Describe in lay terms, completely detailing the research activities that will be conducted by Mayo Clinic staff under this protocol.*

Data collection and Outcome Metrics :

- CAM-ICU scores in the post-operative setting
- Incidence of acute delirium in the post-operative setting
- Time of intravenous sedation in the post-operative setting
- Time of mechanical ventilator in the post-operative setting
- Incidence of anti-psychotic medication administration to treat delirium
- Incidence and duration of cardiopulmonary bypass “pump time”
- Metrics will be stratified based on type of operative procedure, operative time, age, gender, necessity for return to operating room prior to initial extubation

The data source will be the electronic medical record. Baseline retrospective data will be collected on patients prior recorded prior to the start date of this IRB submission; prospective patients undergoing simulation session will have data recorded post IRB start date. Data collection form attached with IRB submission.

Charts of all initial post cardiac surgery patients admitted directly to the ICU who meet the above criteria will be reviewed.

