### **Subject Information**

*Target accrual is the proposed total number of subjects to be included in this study at Mayo Clinic. A “Subject” may include medical records, images, or specimens generated at Mayo Clinic and/or received from external sources.*

Target accrual: 50 historic patients for baseline metric; 50 current intervention patients to undergo simulation session.

Subject population (children, adults, groups): Adult

Inclusion Criteria: Baseline normal neurological function pre-operatively, planned use of mechanical ventilator with endotracheal tube post-operatively after planned cardiothoracic surgical procedure. Age: greater than 18 and less than 60.

**Exclusion Criteria:** Chronic dementia, Alzheimer's disease, or other chronic neurological disease (i.e. Bi-Polar). Chronic use of neurological altering medications such as benzodiazepines, psychotropic, anti-depressants, anxiolytics. Patient undergoing emergent surgery. Use of post-operative cardiopulmonary support devices such as ECMO (extracorporeal membrane oxygenation), intra-aortic balloon pump, total artificial heart, or other similar device. Age greater than 60; Age less than 18. Previous admission to an intensive care unit (intervention patients).

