### Data Analysis

*Power analyses may not be appropriate if this is a feasibility or pilot study, but end-point analysis plans are always appropriate even if only exploratory. Provide all information requested below, or provide justification if not including all of the information.*

**Power Statement:** Based on the literature indicating incidence of post-operative delirium in the post cardiothoracic surgical population and initial power analysis calculations, initial calculations indicate sample size of approximately 30 patients. Therefore, to accommodate for patient loss to follow-up will aim for sample size of 50 patients.

**Data Analysis Plan:** A comparative analysis of the outcome metrics described in the "Study Design and Methods" section will be completed between the pre-implementation baseline data and the post-implementation intervention data. This analysis will evaluate the effect of the multi-sensory ICU simulation experience on post-operative delirium in the cardiac surgical population. An additional post-implementation interview/survey will be conducted on post-intervention patients as described above.

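### The Endpoints section gives a study-end condition as Primary and nothing as Secondary, so no outcome is named to decide the hypothesis, and no metric is identified as its severity half

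*Protocol*

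**What the plan says.** The protocol has one Endpoints section. Its Primary entry is "Study to end when sample sizes are obtained" and its Secondary entry is None.

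The outcomes appear elsewhere:

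- **Research Question and Aims, hypothesis:** "A pre-ICU simulation session will decrease the incidence and severity of post-operative delirium in the ICU". Two aspects of delirium are named, neither ranked above the other.
- **Research Question and Aims, background:** the baseline phase is to establish "current delirium rates (CAM-ICU") and other ICU outcome metrics, among them restraint use and ICU and hospital length of stay.
- **Study Design and Methods:** an unranked list that includes "CAM-ICU scores in the post-operative setting" and, as a separate bullet, the incidence of acute delirium. It also has sedation time, ventilator time and antipsychotic use for delirium.
- **Data Analysis, power statement:** "Based on the literature indicating incidence of post-operative delirium in the post cardiothoracic surgical population".
- **Data Analysis, analysis plan:** "A comparative analysis of the outcome metrics described in the" Study Design and Methods section, between baseline and intervention patients, to evaluate the effect on post-operative delirium.
- **Subject Information, target accrual:** "50 historic patients for baseline metric; 50 current intervention patients to undergo simulation session".

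**The concern.** The field meant to name the deciding outcome holds a rule for when recruitment stops, which duplicates the purpose of the target accrual entry. A reader can see that delirium is the target and that incidence is the most strongly indicated measure of it, but has to infer this.

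The severity half of the hypothesis is less clear still. The word is used for delirium only in the hypothesis. CAM-ICU scores stand beside incidence in the metrics list with no scale, time point or summary, and the background ties CAM-ICU to delirium rates. The scores could be the intended severity measure or simply the raw data from which incidence is derived.

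The baseline data are retrospective, so half of the comparison can be known before anyone settles which result counts. With nothing designated, a report could call the hypothesis supported on CAM-ICU scores while incidence, the basis of the sample size, shows no difference.

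**Working it through.** **1. Is an outcome designated anywhere?** Setting the sections side by side:

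| Section | What it gives | Names a primary outcome? |
|---|---|---|
| Endpoints | Accrual condition; None | No |
| Hypothesis | Incidence and severity | No, two aspects, unranked |
| Study Design and Methods | Unranked list of metrics | No |
| Power statement | Literature incidence of delirium | Implied, not stated |
| Analysis plan | All listed metrics; effect on delirium | No |

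Incidence is indicated by the power statement and by the background's use of CAM-ICU for rates. It is designated nowhere.

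**2. Is severity tied to a metric?** No. The only candidate in the metrics list is CAM-ICU scores, and the text supports either role for it.

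**3. What could the ambiguity cost in false claims?** The protocol gives no figure to reproduce here, and no significance level. Assumptions: two-sided 5% for each measure, no true effect on either, approximately normal test statistics that are not negatively correlated, and two measures, both listed (incidence and CAM-ICU scores). The hypothesis is directional, so only the favourable tail of 0.05 / 2 = 0.025 can be called support.

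- One designated primary: 0.025.
- Success on either measure, independent tests: 1 − 0.975² = 0.0494.
- Success on either measure, correlation 0.8: 0.025 for incidence plus 0.0141 for scores favourable while incidence is not significant (from simulation) = 0.0391.
- Success on either measure, correlation approaching 1 (scores are only the source of incidence): the two tests become one, and the total approaches 0.025.
- Both measures required, independent: 0.025² = 0.0006.
- Both measures required, correlation 0.8: 0.025 − 0.0141 = 0.0109.

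The rate is therefore between 2.5% and about 4.9% if either measure suffices, and below 2.5% if both are required. The protocol does not say which rule applies.

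**The case against.** The strongest objection concerns the hypothesis. It joins incidence and severity with "and", and on its plain wording both should fall. A change in CAM-ICU scores alone would then not support it, and the false-claim rate is lower than with a single primary, not higher. This stands: the inflation is conditional on an either/or reading that the protocol does not state. It does not remove the defect, because a conjunctive test also needs an identified severity measure, and there is none.

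Several stronger readings are tempting, and the document does not support them:

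- **A larger inflation from a third, separate severity measure.** No section lists such a measure, so no figure should rest on it.
- **None under Secondary as a second, independent contradiction of the analysis plan.** The Primary entry suggests the authors took endpoint to mean the point at which the study ends. On that reading None means no further ending condition. It is more likely one misread field than two errors.
- **Bypass use and pump time as a mis-specified outcome.** The list is openly headed as combining data collection with outcome metrics. Sorting covariates from outcomes within it is minor.
- **A breach of a commitment by the sponsor.** The Data Analysis section does say that "end-point analysis plans are always appropriate even if only exploratory", but this is the form's instruction text.

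One might also say that the matter belongs to a statistical analysis plan that is not at hand. Detail may be left to such a plan. Here, though, the protocol has its own Primary field and fills it with something that is not an outcome.

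**Conclusion.** The point holds and should be fixed. The Endpoints section contains wrong content, no outcome is designated to decide the hypothesis, and the severity half of the hypothesis has no identified measure. This follows from the text and depends on no calculation.

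The numerical consequence is modest and conditional: at most about 4.9% against 2.5%, under the assumed 5% level, two listed measures, and a rule that success on either is enough. It shrinks towards zero as the measures coincide and is absent if both must improve. These figures cover chance only and say nothing about bias from comparing historical with current patients.

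A reader might infer that the trial has no outcome at all. That goes too far: delirium is plainly the target, and incidence is the measure most strongly indicated.

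**What to change.** 1. Move the accrual sentence from Endpoints to Target accrual under Subject Information.
2. Enter as Primary: per-patient incidence of post-operative delirium by CAM-ICU, defined in the same way in both groups. This is the quantity the power statement already rests on. The sponsor supplies the definition.
3. Enter as Secondary, marked supportive, the other outcomes named in the background and methods: CAM-ICU scores, intravenous sedation time, ventilator time, antipsychotic administration for delirium, restraint use, and ICU and hospital length of stay. Restraint use and length of stay are called outcome metrics in the background but are missing from the methods list to which the analysis plan refers, so they should be added there too.
4. State which measure represents severity, or state that severity is supportive only.
5. Make these changes before the prospective outcomes are read.

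The cost is protocol wording, with no new patients or data. The trade-off is that the hypothesis is decided on incidence alone and its severity half becomes supportive, which is a choice for the sponsor. Historical-control bias is unaffected.
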